9.2.1.2.7. Thyroid C-Cell Hyperplasia and C-Cell Neoplasms

Individuals with personal or family history of certain thyroid or nonthyroid endocrine abnormalities or certain preexisting laboratory and genetic characteristics will be excluded from the study (see Section 6.2). The assessment of thyroid safety during the trial will include reporting of thyroid TEAEs and measurements of calcitonin according to Section 2 at screening

and Visit 10 (end of treatment) or ET visit. The purpose of calcitonin measurements is to assess the potential of LY3298176 to affect thyroid C-cell function, which includes development of C-cell hyperplasia and neoplasms.

Patients who develop serum calcitonin increases $\geq 50\%$ of the mean of the screening values AND an absolute value ≥ 20 pg/mL and < 35 pg/mL at Visit 10 (end of treatment) or at ET will be asked to repeat the measurement within 1 month. If this repeat value is increasing ($\geq 10\%$ increase), the patient will be encouraged to undergo additional endocrine assessment and longer term follow-up by an endocrinologist to exclude a serious adverse effect on the gland.

For patients who require additional endocrine assessment because of increased calcitonin concentration per criteria provided in this section, data from the follow-up assessment will be collected in the specific section of the eCRF.

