6.2. Exclusion Criteria

Patients will be excluded from study enrollment if they meet any of the following criteria at screening:

Medical Conditions

- [9] Have type 1 diabetes mellitus or latent autoimmune diabetes in adults.
- [10] Have uncontrolled diabetes defined as an episode of ketoacidosis or hyperosmolar state requiring hospitalization.
- [11] Have had an episode of severe hypoglycemia, as defined by the occurrence of neuroglycopenic symptoms requiring the assistance of another person for recovery, within 6 months prior to Visit 1, or have a history of hypoglycemia unawareness or poor recognition of hypoglycemic symptoms. Any patient that the investigator feels will not be able to communicate an understanding of hypoglycemic symptoms and the appropriate treatment of hypoglycemia should also be excluded.
- [12] Have a history of acute or chronic pancreatitis or elevation in serum lipase/amylase (greater than 2 times the upper limit of normal [$>2 \times \text{ULN}$]) or fasting serum triglyceride level of >500 mg/dL at screening.
- [13] Have a diagnosis of gastroparesis or history of bariatric surgery or a clinically significant gastric emptying abnormality, in the opinion of the investigator.
- [14] Have active proliferative diabetic retinopathy.
- [15] Have known liver disease, obvious clinical signs or symptoms of liver disease, acute or chronic hepatitis, or alanine aminotransferase (ALT) levels $>2.5 \times \text{ULN}$ at Visit 1, as determined by the central laboratory at screening.
- [16] Have a known self or family history (first-degree relative) of multiple endocrine neoplasia type 2A or type 2B, thyroid C-cell hyperplasia, or medullary thyroid carcinoma.
- [17] Evidence of hypothyroidism or hyperthyroidism based on clinical evaluation and/or an abnormal thyroid-stimulating hormone that, in the opinion of the investigator, would pose a risk to patient safety. Subjects on a stable dose of thyroid replacement therapy for at least the prior 3 months who are clinically euthyroid and who are anticipated to remain on this dose throughout the trial period may be eligible if they meet the other criteria.

- [18] Have a screening calcitonin ≥ 20 pg/mL as determined by the central laboratory at Visit 1.

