9.2. Adverse Events

Investigators are responsible for monitoring the safety of patients who have entered this study and for alerting Lilly or its designee to any event that seems unusual, even if this event may be considered an unanticipated benefit to the patient.

The investigator is responsible for the appropriate medical care of patients during the study.

Investigators must document their review of each laboratory safety report.

The investigator remains responsible for following, through an appropriate health care option, AEs that are serious or otherwise medically important, considered related to the investigational product or the study, or that caused the patient to discontinue the investigational product before completing the study. The patient should be followed until the event resolves, stabilizes with appropriate diagnostic evaluation, or is reasonably explained. The frequency of follow-up evaluations of the AE is left to the discretion of the investigator.

Lack of drug effect is not an AE in clinical studies, because the purpose of the clinical study is to establish drug effect.

After the ICF is signed, study site personnel will record via eCRF the occurrence and nature of each patient's preexisting conditions, including clinically significant signs and symptoms of the disease under treatment in the study. In addition, site personnel will record any change in the condition(s) and any new conditions as AEs. Investigators should record their assessment of the potential relatedness of each AE to protocol procedure or investigational product via eCRF.

The investigator will interpret and document whether or not an AE has a reasonable possibility of being related to study treatment, study device, or a study procedure, taking into account the disease, concomitant treatment, or pathologies.

A "reasonable possibility" means that there is a cause-and-effect relationship between the investigational product, study device, and/or study procedure and the AE.

The investigator answers yes/no when making this assessment.

In addition to records of observations made at specific times, unexpected signs and symptoms and concomitant medications will be recorded in the clinical trial records throughout the study.

Planned surgeries and nonsurgical interventions should not be reported as AEs unless the underlying medical condition has worsened during the course of the study.

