9.4.3. Laboratory Tests

For each patient, laboratory tests detailed in Appendix 2 should be conducted according to the Schedule of Activities (Section 2).

Any clinically significant findings from laboratory tests that result in a diagnosis and that occur after the patient receives the first dose of investigational product should be reported to Lilly or its designee as an AE.

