9.4.4. Safety Monitoring

Lilly will periodically review evolving aggregate safety data within the study by appropriate methods. In addition, the study team will review safety reports in a blinded fashion according to the schedule provided in the Trial-Level Safety Review plan. Lilly will also review SAEs within time frames mandated by company procedures. The Lilly CRP/CRS will, as appropriate, consult with the functionally independent Global Patient Safety therapeutic area physician or clinical scientist.

In addition, specific safety measures are included in the protocol to ensure appropriate monitoring of pancreatic, thyroid, and liver safety. Laboratory findings that trigger pancreatic and thyroid safety monitoring per Lilly standards are provided in Sections 9.2.1.2.5 and 9.2.1.2.7, respectively. Details of liver safety monitoring are provided in Section 8.1.1. If a study patient experiences elevated ALT $\geq 3 \times$ ULN or elevated total bilirubin $\geq 2 \times$ ULN, clinical and laboratory monitoring should be initiated by the investigator. Details for hepatic monitoring depend upon the severity and persistence of observed laboratory test abnormalities. To ensure patient safety and comply with regulatory guidance, the investigator is to consult with the Lilly CRP/CRS regarding collection of specific recommended clinical information and follow-up laboratory tests (see Appendix 4).

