Appendix 1. Abbreviations and Definitions

Term	Definition
ADA	antidrug antibodies
AE	adverse event: Any untoward medical occurrence in a patient or clinical investigation subject administered a pharmaceutical product that does not necessarily have a causal relationship with this treatment. An adverse event can therefore be any unfavorable and unintended sign (including an abnormal laboratory finding), symptom, or disease temporally associated with the use of a medicinal (investigational) product, whether or not related to the medicinal (investigational) product.
AESI	adverse event of special interest
ALP	alkaline phosphatase
ALT	alanine aminotransferase
ANCOVA	analysis of covariance
AST	aspartate aminotransferase
blinding/masking	
A single-blind study is one in which the investigator and/or his staff are aware of the treatment but the patient is not, or vice versa, or when the sponsor is aware of the treatment but the investigator and/his staff and the patient are not.
 
A double-blind study is one in which neither the patient nor any of the investigator or sponsor staff who are involved in the treatment or clinical evaluation of the subjects are aware of the treatment received.

BG	blood glucose
BMI	body mass index
BP	blood pressure
CFBL	change from baseline
CIOMS	Council for International Organizations of Medical Sciences
complaint	A complaint is any written, electronic, or oral communication that alleges deficiencies related to the identity, quality, purity, durability, reliability, safety or effectiveness, or performance of a drug or drug delivery system.
CRF	case report form
CRP	clinical research physician: individual responsible for the medical conduct of the study. Responsibilities of the CRP may be performed by a physician, CRS, global safety physician, or other medical officer.
CRS	clinical research scientist

CT	computed tomography
CV	cardiovascular
documented symptomatic hypoglycemia	Defined as any time a patient feels that he/she is experiencing symptoms and/or signs associated with hypoglycemia, and has a plasma glucose level of ≤ 3.9 mmol/L (≤ 70 mg/dL).
DPP-4i	dipeptidyl peptidase 4 inhibitor (an OAM)
ECG	electrocardiogram
eCRF	electronic case report form
EDTA	ethylenediaminetetraacetic acid
enroll	The act of assigning a patient to a treatment. Patients who are enrolled in the trial are those who have been assigned to a treatment.
eGFR	estimated glomerular filtration rate

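### Protocol 9.2.1.2.7 asks for a repeat calcitonin from 20 to below 35 pg/mL but names no calcitonin-specific action at 35 pg/mL or more

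*Protocol*

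**What the plan says.** The rule in Protocol 9.2.1.2.7 has three linked parts.

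- **Repeat.** It applies when calcitonin has risen by at least 50% over the mean of the screening values and is at least 20 "pg/mL and < 35 pg/mL at Visit 10 (end of treatment) or at ET will be asked to repeat the measurement within 1 month".
- **Referral.** If that repeat is at least 10% higher, "the patient will be encouraged to undergo additional endocrine assessment and longer term follow-up by an endocrinologist".
- **Data.** A specific eCRF section takes follow-up data for patients who "require additional endocrine assessment because of increased calcitonin concentration per criteria provided in this section".

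Protocol 9.4.4 adds no thyroid trigger of its own: "Laboratory findings that trigger pancreatic and thyroid safety monitoring per Lilly standards are provided in Sections 9.2.1.2.5 and 9.2.1.2.7, respectively". Exclusion criterion 18 in Protocol 6.2 bars a screening calcitonin of at least 20 "pg/mL as determined by the central laboratory at Visit 1". In the Schedule of Activities calcitonin appears at screening, Visit 10 and ET, but not at Visit 801.

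SAP 6.10.4.6 lists every patient with a rise of at least 50% and a value of at least 20 pg/mL, with no upper limit. It sorts them into 20 to below 35, 35 to below 50, and 50 pg/mL or more. That is reporting, not patient follow-up.

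**The concern.** A follow-up rule meant to detect C-cell effects should not stop at its higher values. Here the upper limit takes out patients at 35 pg/mL or more. They miss the repeat, and therefore also the referral step that depends on it and the eCRF section tied to these criteria. No reason for the limit is given. By contrast, the pancreatic enzyme trigger in Protocol 9.2.1.2.5 (at least 3 times the upper limit of normal) has no ceiling.

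At stake is whether a marked calcitonin rise found at the end of treatment gets a confirming measurement, and whether the result reaches the trial database. No endpoint or efficacy estimate is involved.

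**Working it through.** The plan states no figure to reproduce. The check is of the text, with some arithmetic.

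**Inputs.** Screening calcitonin below 20 pg/mL (Protocol 6.2, criterion 18). Rise of at least 50%, value from 20 to below 35 pg/mL, further rise of 10% (Protocol 9.2.1.2.7). Visit 10 on Day 84 and Visit 801 on Day 105, each ±3 days (Table GPGF.1). 92 patients randomized (Protocol 10.1).

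**1. Does a patient at 35 pg/mL or more meet the 50% condition?** The smallest possible ratio exceeds 35/20 = 1.75, a rise of more than 75%. The condition is always met, so only the upper limit excludes the patient.

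**2. Where does the rule act?** A value v qualifies if the screening mean is at most v/1.5.
- v = 25: 25/1.5 = 16.7. The rule acts only if screening was about 16.7 or lower.
- v = 30: 30/1.5 = 20. Every eligible patient from 30 to below 35 qualifies.
- v = 35 or more: nobody qualifies.

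The limit works on the level, not the rise. From 2 to 34 pg/mL (34/2 = 17, +1600%) is inside the rule. From 19.9 to 36 pg/mL (36/19.9 = 1.81, +81%) is outside it.

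**3. Does another provision name an action at 35 pg/mL or more?**

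| Provision | What it gives | What it does not give |
|---|---|---|
| Protocol 9.2 | Documented review of each laboratory safety report; duty to tell the sponsor of anything unusual; for serious, medically important or related AEs, "The patient should be followed until the event resolves, stabilizes with appropriate diagnostic evaluation, or is reasonably explained" | A named retest or referral; beyond the review, action depends on the investigator's judgement |
| Appendix 1 | An AE can be "any unfavorable and unintended sign (including an abnormal laboratory finding), symptom, or disease" | An instruction to treat a calcitonin value as an AE |
| Protocol 9.4.3 | AE reporting of "Any clinically significant findings from laboratory tests that result in a diagnosis" | A route to the diagnosis |
| Protocol 8.1.1 and 9.2.1.2 | Immediate sponsor alert for a laboratory value if the investigator thinks drug should stop for good | A retest; at Visit 10 the last dose has already been given |
| Protocol 8.1.1 | Drug stopped if an exclusion criterion develops | A retest; criterion 18 names a screening value |
| Protocol 9.4.4 and SAP 7.3 | Sponsor review of safety data, including laboratory data | A calcitonin threshold or patient-level action |

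None names a calcitonin-specific action.

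**4. Can the repeat use an existing visit?** Visit 801 minus Visit 10 is 105 − 84 = 21 days, or 15 to 27 days with both windows. Protocol 5.1 instead places follow-up about 4 weeks after the last on-treatment visit: 28 days, or 22 to 34 with the same windows. Table GPGF.1 footnote d and Protocol 9.10 both time Visit 801 from the last dose, which supports the shorter interval.

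**5. What if only the upper limit were deleted?** The repeat would then cover high values, but the 10% referral condition would carry over. From 60 pg/mL, referral would need 60 × 1.10 = 66; a repeat of 65 is 65/60 = +8.3% and would not qualify.

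**6. Size.** 1/92 = 1.1% per affected patient. The documents give no expected rate.

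**The case against.** The strongest reply is that the general safeguards are broad. Under Protocol 9.2 investigators must document their review of every laboratory safety report, are responsible for medical care, and must alert the sponsor to anything that seems unusual, with no condition about stopping drug. The sponsor reviews laboratory data during the trial, and SAP 7.3 mentions a central-laboratory alert document that is not in the file and might cover calcitonin. The value arises after the last dose or at ET, so the gap does not prolong exposure.

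This stands as a limit on the consequence. A reader might infer that a patient at 35 pg/mL or more would go unfollowed or unrecorded. The documents do not support that: the duties above apply, and the Visit 10 or ET value is captured and listed under SAP 6.10.4.6. The reply does not close the gap, because none of these provisions names a retest or referral, while the protocol prescribes a retest at lower values.

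Two further objections also stand. It is tempting to say that the rule acts at 25 pg/mL and skips 60, but at 25 it acts only from a screening value of about 16.7 or lower. It is also tempting to say that 35 pg/mL should lead straight to an endocrinologist, but no such standard appears in the documents; the SAP's cut-points at 35 and 50 are reporting categories.

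**Conclusion.** The gap is real and narrow. As written, an eligible patient at 35 pg/mL or more at Visit 10 or ET has risen by more than 75% and is excluded from the repeat solely by the upper limit. Referral and the dedicated eCRF section follow only from that rule. Follow-up is then left to general duties and sponsor review.

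The 75% figure assumes a screening mean below 20 pg/mL. That holds with the single scheduled screening value. It could fail if a first value of 20 or more were retested under Protocol 6.4 and both values were averaged, or if a patient were enrolled in error.

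The protocol's window coincides with the lowest SAP band, so a reader might infer that higher tiers were dropped by mistake. The documents do not say so, and the point does not need it.

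Few patients are likely to be concerned, and the sample size and efficacy analysis are unaffected. This is a cheap improvement to a safety rule, worth making, and not a threat to the trial's conclusions.

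**What to change.** Keep the existing rule and add one sentence to Protocol 9.2.1.2.7, for example: *Patients with a rise of at least 50% and a calcitonin value of 35 pg/mL or more at Visit 10 or ET will also be asked to repeat the measurement, within 1 month at the latest, and the results will be collected in the same eCRF section.*

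The sponsor's medical team should also state the referral rule for this band. Direct endocrine referral without a further 10% rise is a reasonable option, but it is a clinical choice and is not derived from the documents. Merely deleting the upper limit would settle that choice by default in favour of the 10% condition.

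The cost is a short amendment with ERB approval and one repeat blood draw in the few patients concerned. For completers the draw can be taken at Visit 801 under the Schedule of Activities; the differing timing in Protocol 5.1 should be borne in mind. ET patients, or anyone for whom an earlier repeat is wanted, would need one extra visit. The SAP does not change.

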9.2.2. Complaint Handling

Lilly collects product complaints on investigational products and drug delivery systems used in clinical studies in order to ensure the safety of study participants, monitor quality, and to facilitate process and product improvements.

Patients will be instructed to contact the investigator as soon as possible if he/she has a complaint or problem with the investigational product or drug delivery system so that the situation can be assessed.

9.3. Treatment of Overdose

For patients with suspected or confirmed overdose with LY3298176, there is no specific antidote. The patient should be watched for GI symptoms and hypoglycemia. Treatment is supportive, depending on the patient's symptoms.

9.4. Safety

9.4.1. Electrocardiograms

For each patient, 12-lead ECGs should be collected according to Section 2. Patients must be supine for approximately 5 to 10 minutes before ECG collection and remain supine, but awake, during ECG collection.

Electrocardiograms should be recorded in triplicate using standardized equipment provided by the sponsor.

Consecutive replicate ECGs will be obtained at approximately 1-minute intervals.

Electrocardiograms may be obtained at additional times, when deemed clinically necessary. Collection of more ECGs than expected at a particular time point is allowed when needed to ensure high-quality records.

Electrocardiograms will initially be interpreted by a qualified physician (the investigator or qualified designee) at the site as soon after the time of ECG collection as possible, and ideally while the patient is still present, to determine whether the subject meets entry criteria and for

immediate subject management, should any clinically relevant findings be identified. Any clinically significant findings from ECGs that result in a diagnosis and that occur after the patient receives the first dose of the investigational treatment should be reported to Lilly or its designee as an AE. The investigator (or qualified designee) is responsible for determining if any change in patient management is needed, and must document his/her review of the ECG printed at the time of evaluation.

After enrollment, if a clinically significant increase in the QT/QTc interval from baseline or other clinically significant quantitative or qualitative change from baseline is identified, the patient will be assessed by the investigator for symptoms (eg, palpitations, near syncope, and syncope) and to determine whether the patient can continue in the study. The investigator or qualified designee is responsible for determining if any change in patient management is needed and must document his/her review of the ECG printed at the time of evaluation from at least 1 of the replicate ECGs from each time point.

All digital ECGs will be obtained using centrally provided ECG machines and will be electronically transmitted to a designated central ECG laboratory. The central ECG laboratory will perform a basic quality control check (eg, demographics and study details) and then store the ECGs in a database. At a future time, the stored ECG data may be overread by a cardiologist at the central ECG laboratory for further evaluation of machine-read measurements or to meet regulatory requirements.

The machine-read ECG intervals and heart rate may be used for data analysis and report-writing purposes, unless a cardiologist overreading of the ECGs is conducted prior to completion of the final study report (in which case, the overread data would be used).

In addition, for each patient, a single ECG will be recorded at screening and if the patient discontinues from the study prematurely (Section 2) for immediate patient management. These ECGs will be stored at the investigation site.

Any treatment-emergent clinically significant ECG finding resulting in a diagnosis should be reported as an AE in the eCRF.

9.4.2. Vital Signs

Sitting BP and PR will be measured using standardized equipment provided by the sponsor. Vital sign measurements should be taken before obtaining an ECG tracing and before collection of blood samples for laboratory testing, at visits where required (see Section 2). The participant should be required to sit quietly for 5 minutes before vital sign measurements are taken. An appropriately sized cuff (cuff bladder encircling at least 80% of the arm) should be used to ensure the accuracy of BP measurements. The arm used for the BP measurement should be supported at heart level. At Visit 1 (screening), to determine which arm should be used to collect BP and PR throughout the study, BP and PR will be measured once in each arm, and the arm that had the higher systolic BP should be used to collect all 3 measurements of both BP and PR at all study visits. For each parameter (PR, systolic BP, and diastolic BP), 3 measurements will be taken using the same arm; the recordings should be taken at least 1 minute apart, and each

measurement of sitting PR and BP will be recorded in the eCRF. Any AE related to changes in BP and PR should be reported.

